2.3 Study Endpoints

2.3.1 Primary PK Endpoints

PK analysis of total serum iron concentration; C_{max} and AUC_{last} in fasted and fed conditions.

2.3.2 Secondary PK Endpoints

1. PK analysis of total serum iron concentration; AUC_{inf} in fasted and fed conditions
2. PK analysis of baseline corrected serum iron concentration; C_{max} , AUC_{last} , AUC_{inf} in fasted and fed conditions
3. PK analysis of maltol and maltol glucuronide in plasma; C_{max} , AUC_{last} in fasted and fed conditions
4. PK analysis of TSAT, TIBC, UIBC, transferrin; C_{max} , AUC_{last} in fasted and fed conditions

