- Mean concentrations at any individual time point will only be calculated if at least half of the subjects have valid values (i.e. quantifiable and not missing) at this time point for each formulation / condition.
- In cases where a mean value is not calculated, due to the above criterion not being met, the mean value will be set to missing for mean plotting purposes and to BLQ for summary table.
- BLQ will be set to zero for maltol and maltol glucuronide and to LLOQ for other analytes for the calculation of these mean values if applicable.

3.5.3 *PK Concentrations*

The observed values for maltol, maltol glucuronide, serum iron, baseline corrected serum iron, TSAT, TIBC, UBIC, and transferrin will be summarized by formulation / condition and by visit/timepoint for FAS Population using the following descriptive statistics: n (the number of subjects), arithmetic mean, standard deviation (SD), geometric mean, coefficient of variation (CV), median, minimum and maximum, and a 90% confidence interval (CI) for the mean.

The observed data for maltol, maltol glucuronide, serum iron (uncorrected and baseline corrected), TSAT, TIBC, UBIC, and transferrin will also be listed by formulation / condition group for each individual subject for FAS Population.

For maltol, maltol glucuronide, serum iron (uncorrected and baseline corrected), TSAT, TIBC, UBIC, and transferrin the mean observed plasma concentrations will be plotted on a linear and semi-logarithmic scale against nominal time range by formulation / condition. Geometric mean observed plasma concentrations and 90% CI will be plotted on a linear scale against nominal time range by formulation/condition. Individual observed concentrations be plotted on a linear and semi-logarithmic scale against actual timepoint for each formulation/condition.

3.5.4 *PK Parameters*

For serum iron, baseline corrected serum iron, maltol, maltol glucuronide, TSAT, TIBC, UBIC and transferrin, the following parameters will be calculated by non-compartmental analysis.

Parameters	Description
C_{\max}	Maximum plasma concentration directly from data
T_{\max}	Time to reach maximum concentration directly from data
λ_z	Apparent first-order terminal elimination rate constant (serum iron, maltol, and maltol glucuronide only)
$t_{1/2}$	Terminal elimination half-life, calculated as $\ln(2)/\lambda_z$ (serum iron, maltol, and maltol glucuronide only)
AUC_{last}	Area under the plasma concentration versus time curve from time zero to last.

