AUC_{inf}	Area under the plasma concentration versus time curve from time zero extrapolated to infinity time (serum iron, maltol, and maltol glucuronide only)

The actual collection times will be used for the calculation of PK parameters. The Linear Up Log Down method (equivalent to the Linear Up/Log Down option in WinNonlin® Professional) will be used in the computation of AUC, if applicable.

The apparent terminal elimination rate constant (λ_z), will not be presented for subjects who do not exhibit a terminal elimination phase in their concentration-time profiles. In order to estimate λ_z , linear regression of concentration in logarithm scale versus time will be performed using at least 3 data points. Uniform weighting will be selected to perform the regression analysis to estimate λ_z .

Generally, the λ_z will not be assigned if one of the following happens:

1. T_{\max} is one of the 3 last data points,
2. The adjusted regression coefficient (R-squared) is less than 0.80,
3. The AUC_{extrap} exceeds 20%,
4. The estimated elimination rate indicates a positive slope, or
5. The terminal elimination phase is not linear (as appears in a semi-logarithmic scale) based on visual inspection.

If the λ_z is not assigned, the values of associated PK parameters (e.g. λ_z , AUC_{inf} , or $t_{1/2}$) will not be calculated.

Parameters will be listed by treatment sequence group for each individual subject and summarized by formulation/condition using the following descriptive statistics: n (the number of subjects), arithmetic mean, SD (standard deviation), geometric mean, geometric CV (coefficient of variation), median, minimum and maximum.

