3.5.5 PK analysis

To compare the pharmacokinetics of ferric maltol capsules and oral suspension under fasted and fed conditions, a subject must have a calculable PK parameter for both formulations under fasted or fed condition.

An ANOVA model will be performed on the ln-transformed PK parameters (C_{\max} , AUC_{last} and AUC_{inf}) of the two formulations including terms for sequence (treatment sequence), treatment (formulation/condition), and period as fixed effects, and subjects nested within a sequence as a

random effect. The estimates will be back-transformed into original scale. The point estimates for ratios and the corresponding 90% CIs will be provided.

The PK parameters analyses will be based on the FAS Population.

The sample SAS code for this analysis is included here for $\alpha = 0.10$:

```
proc mixed;
  class subject treatment sequence period;
  model logPKvar = treatment sequence period /ddfm=Satterthwaite; random
  subject(sequence);
  lsmeans treatment/pdiff cl alpha=0.1;
  run;
```

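### AUCinf, terminal slope and half-life are planned for total serum iron, which carries an endogenous level, while SAP 3.5.4 leaves it unclear whether baseline-corrected AUCinf is calculated at all

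*SAP*

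**What the plan says.** SAP 2.3.2 item 1 (and Protocol 6.4 item 1) is "PK analysis of total serum iron concentration; AUC_{inf} in fasted and fed conditions". Item 2 asks for Cmax, AUClast and AUCinf of baseline-corrected serum iron.

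SAP 3.5.4 opens with "For serum iron, baseline corrected serum iron, maltol, maltol glucuronide, TSAT, TIBC, UBIC and transferrin, the following parameters will be calculated" by non-compartmental analysis, so the two iron series are separate entries. Its table then restricts the slope: "Apparent first-order terminal elimination rate constant (serum iron, maltol, and maltol glucuronide only"). Half-life carries the same restriction, and AUCinf is the area "from time zero extrapolated to infinity time (serum iron, maltol, and maltol glucuronide only"). SAP 3.5.3, by contrast, writes "serum iron (uncorrected and baseline corrected), TSAT, TIBC, UBIC, and transferrin", where serum iron covers both series.

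The slope "will not be presented for subjects who do not exhibit a terminal elimination phase". It is also generally not assigned if Tmax is among the last three points, adjusted R-squared is below 0.80, the slope is positive, the terminal phase looks non-linear, or "The AUC_{extrap} exceeds 20" per cent. Half-life and AUCinf are then not calculated.

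SAP 3.5.5 fits a mixed-model ANOVA to ln Cmax, ln AUClast and ln AUCinf without naming analytes, and for the comparison "a subject must have a calculable PK parameter for both formulations under fasted or fed condition".

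SAP 3.2 defines baseline per period. Neither document gives the subtraction formula or says what happens to corrected values at or below zero; the rules in SAP 3.5.2 cover only missing values and values below the quantification limit.

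**The concern.** A terminal slope fitted to total iron mixes the decline of the absorbed increment with a level that does not decay. Dividing the 24 h concentration by that slope adds an area that is mostly endogenous iron and has no meaning as exposure from a 30 mg dose.

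Three things are at stake. A listed secondary endpoint, with an ANOVA implied for it, may rest on a handful of subjects. Those subjects may differ in profile shape from the rest. And the more interpretable version, corrected AUCinf, may not be programmed if the restriction in SAP 3.5.4 is taken literally. In an open-label study, the scope and the rule for non-positive values are better fixed before the data are seen than after.

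**Working it through.** The documents state no figure for how often AUCinf will be calculable, so there is none to reproduce.

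**1. What the 20% screen demands.** The extrapolated share is (C24/λz) / (AUClast + C24/λz). A share of at most 20% means C24/λz ≤ 0.25 × AUClast. Let the mean concentration over 24 h be m times C24, so AUClast = 24 × m × C24. Then λz ≥ 1/(6m), half-life ≤ 6m × ln 2 = 4.16m hours, and a log-linear fall from 6 to 24 h implies C6/C24 = exp(18/(6m)) = exp(3/m).

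- m = 1.25: half-life at most 5.2 h, C6/C24 about 11.0
- m = 1.5: at most 6.2 h, about 7.4
- m = 2: at most 8.3 h, about 4.5

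At least three points are needed, so the 6, 10 and 24 h samples always enter the regression. Total iron that settles back to its pre-dose level cannot easily fall that steeply.

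**2. Assumed profiles.** Endogenous level 1 plus a one-compartment increment, at the 12 planned sampling times, with linear-up/log-down AUC. The slope was chosen by best adjusted R-squared (my choice; the SAP gives no rule for picking points). Visual inspection was not modelled.

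- Noise-free grid: absorption rate 0.5, 1, 2 per h; half-life 2, 3, 4, 6, 8, 12 h (18 profiles per peak).
- Pairs: absorption rate 1 per h; half-life 3 and 6 h; assay CV 5 and 10%; endogenous level drifting to a 24 h factor with CV 30 or 50%, either independent or shared between a subject's two formulations.
- Upper bound: 32 × the pass rate for one formulation; in brackets, the bound on a wider grid of absorption rate and half-life.

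| Peak / baseline | Extrapolated share, noise-free | Profiles meeting 20% | Expected pairs of 32 | Upper bound |
|---|---|---|---|---|
| 1.25 | 79-88% | 0 of 18 | 0-1 | - |
| 2 | 49-64% | 0 of 18 | 0-1 | - |
| 3 | 33-52% | 0 of 18 | 0-4 | 5 (7) |
| 4 | 24-45% | 0 of 18 | 0-9 | 10 (14) |
| 5 | 19-42% | 2 of 18 | 1-14 | 16 (19) |

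A separate calculation with other assumptions (8% noise, between-subject spread in rise and half-life, milder drift) made AUCinf calculable in 0% of profiles at 1.5x, 0.1-1% at 2x, 3-13% at 3x and 20-47% at 5x.

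**3. Selection.** In the first model at 3x, the median 24 h/pre-dose ratio is 0.47-0.66 in calculable profiles against 1.01-1.19 in all. In the second model the geometric mean endogenous 24 h/pre-dose ratio is 0.90 in all profiles. Among calculable ones it is 0.66 at 2x, 0.74-0.77 at 3x and 0.82-0.83 at 5x. The direction agrees; the size depends on the drift assumed.

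**4. Large peaks.** In the first model at 10x (5% noise), 74-96% of profiles pass, and the median ratio is 1.00-1.78 in passers against 1.07-1.85 in all. Sparsity and selection have largely gone.

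**5. Precision.** If the planning SD of 0.38 (Protocol 12.1, set for Cmax and AUClast) also held for AUCinf, a simple paired 90% interval around a ratio of 1 is exp(± t(0.95, k-1) × 0.38/√k):

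- k = 5: exp(± 2.132 × 0.170) = 0.70-1.44
- k = 10: exp(± 1.833 × 0.120) = 0.80-1.25
- k = 16: exp(± 1.753 × 0.095) = 0.85-1.18
- k = 32: exp(± 1.696 × 0.067) = 0.89-1.12

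This is a guide only; the SAP model pools four treatments.

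**6. Corrected iron.** After subtracting the pre-dose value, noise-free extrapolated shares are about 0%, 0.5% and 7% at half-lives of 1.5, 3 and 6 h, so all pass. With noise, corrected AUCinf is calculable in 25-100% of profiles without drift and in 16-94% with drift. The corrected 24 h value is zero or negative in 0-49% and 7-50% respectively (19-66% in the second model). In those profiles, integrating zeros to 24 h gives a median corrected AUClast 15-43% higher than stopping at the last positive value.

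**The case against.** The strongest reply is that the plan contains the damage. AUCinf is secondary and no acceptance limit is tied to it. The screens withhold poor values, and n is reported with the parameters and the ratios, so a thin table would be visible. This stands, and it answers a reader who might infer that misleading total-iron AUCinf values will be widely reported, or that the capsule-suspension conclusion is at risk. It does not answer why an ANOVA should be implied for a quantity without a clear meaning.

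Sparsity is a projection. The documents give no iron levels, half-life or drift, and the word *generally* leaves the analyst discretion. This also stands. A reader might further infer that qualifying pairs are selected whatever the peak; the 10x result shows otherwise.

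On wording, SAP 2.3.2 item 2 and Protocol 4 and 12.2 plainly intend corrected AUCinf, and SAP 3.5.3 uses serum iron as an umbrella term. So the documents do not show that the SAP has dropped it, only that a programmer could read the restriction either way.

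Corrected AUCinf will also be incomplete, so it is no clean substitute. Finally, Protocol 4 and 12.2 list AUCinf, slope and half-life for TSAT, TIBC, UIBC and transferrin, which SAP 3.5.4 omits. Because the endpoints for those markers are only Cmax and AUClast, and Protocol 12.2 defers full details to the analysis plan, this is mostly an acceptable refinement.

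**Conclusion.** The point holds as a should-fix on a secondary endpoint. Two parts rest on the text and on principle: extrapolated total iron does not measure exposure from the dose, and the scope of SAP 3.5.4, read literally, conflicts with endpoint 2. The rule for non-positive corrected values is missing.

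The size is conditional on assumed profiles: few calculable pairs at peaks up to about 3-4x baseline, selected on shape, with both effects fading by about 10x. Cmax and AUClast of total iron, their four confidence intervals and the sample size are not touched. Nor do the documents require that the total-iron endpoint be removed; making it descriptive is enough.

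**What to change.** 1. In SAP 3.5.4, restrict slope, half-life and AUCinf to baseline corrected serum iron, maltol and maltol glucuronide. In SAP 3.5.5, name the analytes and run the AUCinf model for corrected iron, not total iron. Keep total-iron AUCinf, if at all, as a descriptive listing with the number calculable, or drop it.
2. State that corrected iron is the value minus that period's pre-dose value. Before database lock, fix one rule for corrected values at or below zero. The Protocol's abbreviation list ends AUClast at the last concentration that can be measured; the rule should agree with that or state the departure. Integrating zeros through to the final sample could be such a departure.
3. Label the corrected AUCinf ratio and its 90% interval as descriptive, because it will also be missing for some subjects.
4. Optionally, note in the SAP that the AUCinf, slope and half-life listed for TSAT, TIBC, UIBC and transferrin in Protocol 4 and 12.2 are not calculated. Only Protocol 12.2 asks for an AUCinf ratio for these markers; Protocol 4 confines ratios to the two iron series.

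The cost is that one secondary parameter loses its formal comparison and the change must be documented. The rest is wording. Selection on profile shape is reduced for corrected iron, not removed.

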5.4.2 Phase I studies in adults

ST10-01-101 study

Another open-label, randomized Phase 1 study evaluated the pharmacokinetics of Ferric Maltol and its effect on iron indices in patients with iron deficiency (with or without anemia). 24 subjects received Ferric Maltol 30, 60, or 90 mg BID over an 8-day period. PK and iron uptake were assessed on Days 1 and 8. Ferric maltol showed predictable pharmacokinetics, no accumulation over 7 days, and improvements in iron uptake across the dose range 30–90 mg BID (Bokemeyer, 2016).

The PK data from this study are consistent with previous data indicating that maltol is rapidly glucuronidated and renally excreted after ST10 dosing, while iron is independently absorbed. Across the three dosing regimens investigated, exposure to maltol glucuronide increased dose proportionally. Serum iron concentrations and TSAT values generally increased with higher doses, but there was no clear relationship between these parameters and exposure to maltol or maltol glucuronide. Higher NTBI levels were detected in the higher dosing regimens. Although the frequency of AEs was also higher with these dosing regimens, there is no evidence that this was a consequence of elevated NTBI in these subjects. The reported AEs were consistent with the established safety profile of ST10.

ST10-01-102 study

The study results showed that plasma and urinary PK parameters for maltol and maltol glucuronide were consistent with rapid metabolism of maltol to maltol glucuronide, followed by renal excretion. Total serum iron and TSAT increased after ST10 dosing, although there was no clear relationship between either of these parameters and exposure profile to maltol or maltol glucuronide. There was no evidence of intact ST10 in serum samples, as measured indirectly by NTBI, and there were no findings in this sub-study that affected the safety profile of ST10.

The low serum NTBI values are consistent with the safety profile of ST10. Unsurprisingly, given the short duration, there were no significant safety findings in this sub-study.

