The Screening Phase will consist of one visit: Study Visit 1 (Screening) scheduled to take place within 14 days prior to the planned Treatment Phase for each subject. The purpose of this visit is to determine subject eligibility for the study.

Prior to the first treatment period, subjects will arrive at the Clinical Unit on Day -1 at least 13 hours before dosing. After at least 10 hours overnight fasting at the Clinical Unit subjects will be randomized to one of the 4 treatment sequences. PK samples will be collected pre-dose and up to 24 hours post-dose during each period (12 times including pre-dose) for the measurements of serum iron, TSAT, TIBC, UIBC, transferrin, plasma maltol and maltol glucuronide.

There will be at least 48 hours washout period between dose administrations. Subjects will fast at least 10 hours prior to each treatment period dosing.

Subjects will stay at the Clinical Unit during the 4 treatment and 3 washout periods and will be discharged on Day 8 following the last PK sampling timepoint.

Post study telephone follow-up will be conducted 3-7 days following Treatment Period 4. During early discontinuation a safety follow up at the Clinical Unit will be performed 3-7 days after the last study medication.

The schedule of procedures can be found in Table 10.2 from Protocol.

2.2.2 *Treatment Assignment and Blinding*

This is an open label study and treatment assignment is not blinded.

The randomization procedure (created using a computer-generated random permutation procedure) will randomize the subject to one of the 4 treatment sequences to either Sequence A Sequence B, Sequence C or Sequence D. The site will dispense the appropriate formulation of open-label ferric maltol bottles at each scheduled PK day according to the schedule of assessments. The randomization scheme will be programmed by Medpace independent statistician using SAS®. Detailed randomization methods and procedures are described in a stand-alone document.

2.2.3 *Study Drug*

Investigational Medicinal Product

Ferric maltol oral suspension: oral suspension containing 30 mg elemental iron, in the form of 231.5 mg ferric maltol, in 5 ml suspension.

Comparator

Ferric maltol capsules: gelatin capsules with 30 mg elemental iron, in the form of 231.5 mg ferric maltol.

2.2.4 *Sample Size Determination*

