3.5 Pharmacokinetic Assessment

3.5.1 *PK blood sampling*

PK samples were to be collected on Day 1 to Day 8, pre-dose and post-dose according to the PK Sample Schedule Group that the subject was assigned to.

On all four PK study days, all subjects will have baseline PK blood samples collected immediately prior to Ferric Maltol dosing (0 hr). Subjects will then have further PK blood samples collected at 11 additional times after dosing; the post-dose PK sample times will be 15 mins \pm 2 min, 30 mins \pm 2 min, 45 mins \pm 5 min, 1 hr \pm 5 min, 1.5 hr \pm 5 min, 2 hrs \pm 5 min, 3 hrs \pm 5 min, 4 hrs \pm 5 min, 6 hr \pm 10 min, 10 hrs \pm 15 min and 24 hrs \pm 15 min.

For each individual subject, the post-dose PK blood sampling schedule will be the same on all four PK days. PK blood samples on the PK days will be: serum iron, total and unsaturated iron binding capacity (TIBC, UIBC), transferrin, transferrin saturation (TSAT), maltol and maltol glucuronide.

3.5.2 *Handling missing PK data or concentration below the lower limit of quantification*

If the actual sampling time is missing, but a valid concentration value has been measured, the concentration value will be flagged, and the scheduled time point may be used for the calculation of PK parameters. If the dosing history information for a subject is missing, the sampling for that subject relative to the missing dose will not be included in the analysis.

Missing concentrations related to serum iron, TSAT, transferrin, TIBC, and UIBC will not be imputed or used in the analysis. If the dosing history information for a patient is missing, the sampling for that patient relative to the missing dose will not be included in the analysis.

For maltol and maltol glucuronide, all drug concentration below the quantifiable limit (BQL) are treated as zero. When more than half (>50%) of the values at a single timepoint are BQL, mean and median values are reported as BQL. Standard deviation and %CV are not reported; maximum and minimum values are reported as observed (including BQL). If, as the result of the calculation (eg. dose normalization, descriptive statistics) a concentration value is less than the LLOQ the value should be reported as <LLOQ value. The following general rules will be applied for the concentration summary (including tabulation and plotting) for each period:

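### UIBC Cmax and Tmax look in the wrong direction: UIBC falls as iron is absorbed, so the response to the dose lies in its minimum

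*SAP*

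**What the plan says.** SAP 2.3.2 lists "PK analysis of TSAT, TIBC, UIBC, transferrin" as its fourth secondary PK endpoint, to be summarised by Cmax and AUClast in both the fasted and the fed state. Protocol 6.4 and the protocol synopsis carry the same item.

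SAP 3.5.4 applies one set of definitions to all analytes, UIBC included. Cmax is "Maximum plasma concentration directly from data", Tmax is the time of that maximum, and AUClast is "Area under the plasma concentration versus time curve from time zero to last". The SAP does restrict λz, half-life and AUCinf to serum iron, maltol and maltol glucuronide, but Cmax and Tmax are the same for every analyte.

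The pre-dose sample is part of each profile. SAP 3.5.1 says that "all subjects will have baseline PK blood samples collected immediately prior to Ferric Maltol dosing (0 hr", and SAP 2.2.1 describes sampling "up to 24 hours post-dose during each period (12 times including pre-dose". Nothing excludes the 0 hr value from Cmax.

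Baseline correction is planned for serum iron alone ("PK analysis of baseline corrected serum iron concentration"). No minimum, change from baseline or baseline correction is defined as a PK parameter for UIBC.

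On the direction of response, protocol 5.4.2 reports for an earlier adult study (ST10-01-102): "Total serum iron and TSAT increased after ST10 dosing".

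**The concern.** UIBC is the unsaturated part of the iron binding capacity. If TIBC is stable over a day, UIBC falls by as much as serum iron rises. For serum iron and TSAT, the observed maximum captures the response to a dose. For UIBC, the observed maximum captures the moment of least iron loading, which is usually before the dose or late in the profile. The response is the minimum.

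A secondary objective is to evaluate PK through UIBC among other markers, and the study is meant to support interchangeability of suspension and capsule. If a suspension/capsule ratio for UIBC Cmax is reported, it will tend to sit close to 1 with a narrow interval whether or not the formulations deliver iron equally. A reader could take that as support for similarity when it says little about absorption.

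**Working it through.** **No plan figure to reproduce.** The documents give no variance, expected value or limit for UIBC. The (80%, 125%) aim in protocol 12.1 covers the four serum iron intervals only.

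**Inputs from the documents:** 12 sampling times from 0 to 24 h, linear-up/log-down AUC, 90% CI, n = 32, and serum iron and TSAT rising after dosing.

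**Inputs assumed:** TIBC 60 and baseline iron 18 µmol/L; peak iron rise R of 3 to 20 µmol/L at about 1.5 to 2 h; iron disappearance 0.35/h or 0.15/h (the slower rate only for R of 6 to 20); diurnal fall in iron 0 or 30%; day-to-day iron SD 15%; assay CV 3%. The relation UIBC = TIBC − serum iron follows from the names of the quantities; the documents do not write it out.

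**Step 1: arithmetic without noise.** Pre-dose UIBC is 60 − 18 = 42. Compare a product that releases no iron with a working product, with iron back at baseline by 24 h and no diurnal change:

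| Rise R | Serum iron Cmax ratio, 18/(18+R) | UIBC Cmax ratio | UIBC minimum ratio, 42/(42−R) |
|---|---|---|---|
| 3 | 18/21 = 0.86 | 42/42 = 1.00 | 42/39 = 1.08 |
| 6 | 18/24 = 0.75 | 42/42 = 1.00 | 42/36 = 1.17 |
| 12 | 18/30 = 0.60 | 42/42 = 1.00 | 42/30 = 1.40 |
| 20 | 18/38 = 0.47 | 42/42 = 1.00 | 42/22 = 1.91 |

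**Step 2: simulation on the SAP's sampling times**, with the variation listed above. Entries are no-iron/working ratios. Ranges run over diurnal fall 0 and 30%. The probability that the 90% CI excludes 1 at n = 32 is in brackets.

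| Disappearance | R | UIBC Cmax | UIBC AUClast | UIBC minimum |
|---|---|---|---|---|
| 0.35/h | 6 | 1.02–1.04 (0.31–0.49) | 1.04 (0.47–0.62) | 1.17 |
| 0.35/h | 12 | 1.03–1.04 (0.59–0.64) | 1.08 (0.95–0.98) | 1.46–1.47 |
| 0.35/h | 20 | 1.05 (0.65–0.87) | 1.13–1.14 (1.00) | 2.37–2.38 |
| 0.15/h | 6 | 1.05 (0.65–0.93) | 1.06–1.07 (0.88–0.95) | 1.16–1.17 |
| 0.15/h | 12 | 1.06–1.09 (0.78–1.00) | 1.14–1.15 (1.00) | 1.45–1.47 |
| 0.15/h | 20 | 1.06–1.12 (0.84–1.00) | 1.26–1.29 (1.00) | 2.31–2.39 |

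Including the smallest rise (R = 3, faster disappearance), the overall ranges are 1.01 to 1.12 for UIBC Cmax, 1.02 to 1.29 for UIBC AUClast and 1.07 to about 2.4 for the UIBC minimum. Serum iron Cmax runs from 0.87 down to 0.48.

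**Step 3: reading the results.**
- UIBC Cmax departs from 1.00 mainly because some iron is still raised late in the profile and because of sampling noise. In every R = 6 to 20 scenario its 90% CI at n = 32 lies inside 80–125% (widest span 0.99 to 1.16), although one product releases no iron at all.
- For a product that releases half the iron (faster disappearance, R of 3 to 20), the UIBC Cmax ratio is 1.00 to 1.02, against 1.03 to 1.77 for the minimum.
- The minimum at R = 20 is 1.91 without noise and about 2.4 in the simulation. The top of that range therefore depends on how much variation is assumed. The direction and ordering do not.

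**The case against.** The strongest reply has four parts.

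1. **The endpoint is not only Cmax.** The same line names AUClast, which does respond to a loss of iron. A reader might infer that the UIBC endpoint as a whole cannot detect a formulation difference; the documents do not support that. The point holds for the Cmax half and for Tmax only.
2. **UIBC Cmax is not empty of information.** It moves by 1 to 12%, and its interval can exclude 1. At the smallest tabulated rise with faster disappearance and no diurnal fall, it does so about as often as AUClast (0.49 against 0.47). Insensitive in size is a fair description; uninformative is not.
3. **No decision rests on it.** UIBC has no acceptance limits. A product that failed to release iron would show in the primary serum iron Cmax and in TSAT Cmax. It is also unclear that a UIBC ratio will be produced: protocol 12.2 plans formulation ratios for every analyte, the synopsis limits them to total and baseline corrected serum iron, and SAP 3.5.5 names no analyte.
4. **The fall in UIBC will be visible anyway.** SAP 3.5.3 plans summaries at each time point, with mean and individual profiles. If TIBC is stable, the UIBC minimum largely repeats serum iron Cmax.

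All four stand, and they limit the consequence. They do not remove the mismatch: a named secondary parameter and its Tmax, as defined, describe the wrong end of the UIBC profile. A summary by nominal time point also does not give each subject's minimum or its timing.

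**Conclusion.** The point holds for UIBC Cmax and Tmax, as a minor matter. Under the assumed values, a total loss of iron release shifts UIBC Cmax by about 1 to 12%, compared with about 7% to more than twofold for the UIBC minimum and about 2 to 29% for UIBC AUClast.

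This rests on UIBC being TIBC minus serum iron, on TIBC being stable within a day, and on iron levels and kinetics that the documents do not give. The size of the contrast changes with those assumptions. The direction follows from the protocol's own report that serum iron and TSAT rise after dosing.

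A reader might go further and infer that a UIBC Cmax ratio near 1 could lead the study to a false conclusion of equivalence. The documents do not support that: the stated aim concerns the four serum iron intervals only, and those would react to a failed product.

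**What to change.** - In SAP 3.5.4, for UIBC only, replace Cmax and Tmax by the minimum observed value and its time (Cmin, Tmin), or by the maximum decrease from the same period's pre-dose value. Keep AUClast.
- Make the matching edit in SAP 2.3.2, protocol 6.4 and the protocol synopsis.
- Cmin fits the log-scale model of SAP 3.5.5 directly. A maximum decrease can be zero or negative, so it would need to be compared on the difference scale.
- While editing, state in SAP 3.5.5 which analytes receive a formulation ratio, so that it agrees with protocol 12.2 and the synopsis.

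The cost is a few lines of wording and a small change to a secondary endpoint, with no new samples or assays. Protocol 12.2 leaves full analysis details to the analysis plan before database lock. The drawback is that the new UIBC result will partly repeat serum iron Cmax when TIBC is stable.
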